11.3.3. Enrollment Feasibility

The planned interim assessments of enrollment feasibility will include a blinded re-assessment of sample size.

At each interim analysis the data for subjects who were enrolled at least 21 days prior to the data cut-off date for the DSMB report will be used to predict the number of subjects that will be evaluable for the per protocol analysis population at the time of the final analysis. If the predicted count for the number of subjects is less than 200, the enrollment target will be inflated sufficiently to reach this target.

It is acknowledged that this is a simplistic approach to sample size re-estimation which is impacted by the uncertainty in the rate estimates. It is also perforce limited in that a blinded analysis does not estimate the current treatment effect, but instead assumes it is equal to that proposed in the study design. This analysis is intended primarily to provide a framework to review the adequacy of the assumptions underlying the trial design and assess the operational feasibility of reaching the enrolment target, and to permit that discussion to take place amongst the blinded study team that is responsible for trial conduct and decision making.

The simulation study described in Section 11.3.2 was extended to assess the impact on the power available for the final analysis when sample size re-estimations as described above are included with the futility analyses at the second and third interim analyses. In the simulation study, multiple scenarios were considered which varied the following parameters:

The true rates of response in each arm (null and alternative hypothesis)

The percentage of subjects eligible for the cocci-positive per-protocol population (10% or 20%)
 The maximum allowable sample size of the trial (1500 or 1250)

Table 10 displays the power of the Z test, the average number of total subjects enrolled across the simulated trials, and the average enrollment target across the simulated trials for each of the scenarios.

Scenarios 1 and 4 correspond to the protocol specified alternative hypothesis in which the arm-specific Day 22 cumulative response is 0.40 and 0.20, and an assumed 20% of subjects are eligible for the per-protocol analysis. Comparing the adaptive design (Table 10) to the fixed sample size design (Table 5), there is little impact of adaption on either power or sample size. Scenarios 2 and 5 correspond to the protocol specified null hypothesis in which the arm-specific Day 22 cumulative response is 0.20 in both arms. In these scenarios, the type I error is preserved at < 5% and the average sample size is about 25% less than that of the fixed sample size of 1000. Scenarios 3 and 6 correspond to the protocol specified alternative hypothesis, but with only half as many subjects eligible for the per protocol analysis (10% versus 20%). In this setting power is increased from 56.9% without sample size re-estimation (not tabulated) to 69.8% or 64.4% corresponding to the limit of 1500 or 1250.

For comparison, if the arm-specific Day 22 cumulative response is 0.30 and 0.10 (attenuated response proportions with protocol-assumed effect size), and an assumed 20% of subjects are eligible for the cocci-positive per-protocol analysis, the power available is 94.7% (not displayed in Table 10). If the arm-specific Day 22 cumulative response is 0.35 and 0.20 (attenuated treatment effect), and an assumed 20% of subjects are eligible for the per-protocol analysis, the power available is 65.3% (not displayed in Table 10).

Table 10: Operating Characteristics of a Trial Design with Both a Futility and Sample Size Assessment at the Three Interim Analyses

Scenario	Power	Average Number of Subjects Enrolled	Average Accrual Goal
1, Fluconazole, Placebo Rates: 0.4, 0.2 Percentage of subjects eligible for cocci-positive PP: 20% Maximum Allowable Sample Size: 1500	87.1	1019	1046
2, Fluconazole, Placebo Rates: 0.2, 0.2 Percentage of subjects eligible for cocci-positive PP: 20% Maximum Allowable Sample Size: 1500	4.6	734	1026

3. Fluconazole, Placebo Rates: 0.4, 0.2 Percentage of subjects eligible for cocci-positive PP: 10% Maximum Allowable Sample Size: 1500	69.8	1336	1430
4. Fluconazole, Placebo Rates: 0.4, 0.2 Percentage of subjects eligible for cocci-positive PP: 20% Maximum Allowable Sample Size: 1250	87.0	1015	1044
5. Fluconazole, Placebo Rates: 0.2, 0.2 Percentage of subjects eligible for cocci-positive PP: 20% Maximum Allowable Sample Size: 1250	4.6	728	1025
6. Fluconazole, Placebo Rates: 0.4, 0.2 Percentage of subjects eligible for cocci-positive PP: 10% Maximum Allowable Sample Size: 1250	64.4	1120	1214

11.4. Final Analysis Plan

11.4.1. Analysis Populations

Safety Analyses:

- Safety population – This safety analysis population includes all subjects who took at least one dose of study medication.

Efficacy Analyses:

- Intent-to-Treat (ITT) population – This efficacy analysis population includes all randomized subjects.
- Cocci Positive Modified Intent-to-Treat (mITT) population – This efficacy analysis population includes all randomized subjects who meet the case definition of coccidioidomycosis pneumonia and took at least one dose of study medication. Note that it is not necessary for a subject to be adherent to study drug to be eligible for inclusion in the mITT population.
- All Randomized Modified Intent-to-Treat (mITT) population – This efficacy analysis population includes all randomized subjects who took at least one dose of study medication regardless of cocci-status. Note that it is not necessary for a subject to be adherent to study drug to be eligible for inclusion in the mITT population.

- Cocci Positive Per-Protocol (PP) population – This efficacy analysis population includes randomized subjects who meet the case definition of coccidioidomycosis pneumonia who were compliant with the intervention administration and have coccidioidal serology data available at the Day 1 and 22 visits.
- All Randomized Per-Protocol (PP) population – This efficacy analysis population includes randomized subjects who were compliant with the intervention administration regardless of cocci-status and have coccidioidal serology data available at the Day 1 and 22 visits.

Adherence is assessed at each study visit depending on the fraction of expected pills taken on or before that time point. If at any visit the subject's cumulative fraction of pills taken drops below 80%, they are deemed non-adherent. This decision is not reversible, even if the subject's cumulative fraction of pills taken rises above 80% at a future visit.

From that visit forward in time, the subject is dropped from the PP analysis populations, and their data after that visit is censored from time to event analysis, and they are dropped from any fixed time point analyses occurring after that visit. Data collected from time points prior to the time point at which a subject becomes non-compliant will still contribute to efficacy analyses. In the unlikely event of an error in randomization or drug distribution, subjects will be grouped by the study product they actually received in the per-protocol and safety analyses, but will be grouped by their intended randomized assignment in the intent-to-treat and modified intent-to-treat analysis.

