Cumulatively, these facilities diagnosed 5,008 cases of CAP in outpatient setting (including primary care outpatient facilities, urgent care facilities, and emergency departments) in 2012. Of these cases, 896 (18%) were known to be tested for coccidioidomycosis, although the proportion tested varied ranged 5% to 39% by facility. Overall, of CAP cases known to be tested, 178 (20%) were reported as coccidioidomycosis positive to respective health department, however, this proportion varied from 7% to 45% by facility, and even various clinic types within the facility. In

general, a smaller proportion of CAP cases seen at emergency departments tested positive for coccidioidomycosis as compared with cases seen at other facility types.

Figure 2: Geographic distribution of Endemic Coccidioidomycosis

<http://www.cdc.gov/fungal/diseases/coccidioidomycosis/>

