- The proportion of subjects who received at least one dose of the intervention and who exhibit an increase in liver function tests from baseline (pre-treatment Day 1) as defined as: confirmed AST elevation of >5X ULN or greater than or equal to 225 IU/L or ALT elevation of >5X ULN or greater than or equal to 250 IU/L or total bilirubin elevation >1.5X ULN or aminotransferase elevation of >3X ULN accompanied by total bilirubin elevation >1.5X ULN.

Exploratory Outcome 8:

- The adherence to long term self-administration of daily medications will be assessed in this order of precedence:
 - First: The mean number of pills taken as assessed by pill-count on Days 22, 29 and 43.
 - Second: Subject self-reported adherence as reported on Days 22, 29 and 43.

Exploratory Outcome 9:

- The proportion of subjects with a detectable fluconazole level as assessed by blood test on Days 22 and 43 in fluconazole recipients.
 - Plasma fluconazole concentration will be determined by high-performance liquid chromatography (HPLC)

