6.6. Concomitant Medications/Treatments

Administration of any medications, therapies, or vaccines will be recorded on the appropriate data collection form. Concomitant medications will include all current medications and medications taken within 30 days prior to signing the informed consent form through Day 43 for all subjects. Prescription and over-the-counter drugs will be included as well as vitamins and supplements.

Use of new medication should prompt evaluation for the presence of a new diagnosis of chronic medical disease or condition.

Any other systemic antifungal not provided as part of the study intervention is prohibited during the treatment period of this study, and prohibited within the 4 weeks prior to enrollment (with the exception of a single dose of fluconazole) as specified in Exclusion Criterion 6.

Medications that might interfere with the evaluation of the investigational product should not be used unless absolutely necessary. Fluconazole is a potent CYP2C9 inhibitor and a moderate CYP3A4 inhibitor. Subjects treated with fluconazole who are concomitantly treated with drugs with a narrow therapeutic window metabolized through CYP2C9 and CYP3A4 should be

considered for additional monitoring of blood levels, lack of efficacy, or increased toxicity of these medications.

The following lists are derived from the FDA package insert and from the information in Up to Date®. It is not a complete list of potential drug-drug interactions, but are lists of agents that are likely to be seen in an ambulatory population.

Antibacterial medications that are prescribed by the health care provider for the treatment of community acquired pneumonia are also not included on this list but are discussed in Section 2.3.1.

Medications in this category include, but are not limited to the following:

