11.2. Sample Size Considerations

11.2.1. Sample Size for Per Protocol Analysis Population

The primary analysis will compare the proportion of subjects achieving clinical response at Day 22 among efficacy evaluable subjects, defined as subjects in the Cocci-Positive Per Protocol analysis population who meet the case definition of coccidioidomycosis pneumonia who were compliant with the intervention administration and have coccidioidal serology data available at the Day 1 and 22 visits. We further assume that the clinical response proportion at Day 22 will be 0.20 in the placebo arm, and 0.40 in the fluconazole arm. As described in section 11.2.3, enrollment will continue until 200 subjects are evaluable for efficacy, 100 in each treatment arm, which suffices for 88% power for the Z test with unpooled variance to compare proportion of clinical responses at Day 22 at the two-sided level of 0.05. This is the primary sample size calculation which forms the basis for target enrollment to the study and for subsequent sample size re-estimation procedures at scheduled interim analyses while the study is enrolling.

A secondary analysis in the Cocci Positive Modified Intent-to-Treat population will compare the proportion of responders at Day 22, treating subjects dropping out before the Day 22 visit as non-responders. Assuming that the probability of drop-out before Day 22 is 20% among cocci-positive subjects, we would expect that 250 cocci-positive subjects would be available for this secondary analysis as a result of reaching the target sample size of 200 cocci-positive subjects with Day 22 follow-up for the primary analysis. Since subjects who drop-out are considered non-responders, the probability of response in the control-arm subjects would be $0.8 * 0.2 = 0.16$, and in the treated subjects would be $0.8 * 0.4 = 0.32$. The Z-test with unpooled variance has power of 85% to detect this difference in response proportions with 125 cocci-positive subjects per arm.

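### The primary per-protocol population has no rule for prohibited antifungal use, so a placebo case who took an outside systemic antifungal before Day 22 can be counted as a placebo responder.

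*Combined protocol and SAP*

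**What the plan says.** Section 6.6 states that "Any other systemic antifungal not provided as part of the study intervention is prohibited during the treatment period of this study".

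Section 11.4.1 defines the Cocci Positive Per-Protocol population as "randomized subjects who meet the case definition of coccidioidomycosis pneumonia who were compliant with the intervention administration and have coccidioidal serology data available". The serology must come from both Day 1 and Day 22. Sections 3.2.1 and 11.4.1 define adherence as at least 80% of expected study pills. A cumulative fraction below 80% is the only stated event that takes a subject out of the per-protocol populations.

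Sections 3.2.1 and 11.4.4.1 code Day 22 response from the FLEET CAP score change alone. Sections 5.3.3.1 and 6.7 take a subject off study treatment when a physician judges that additional therapy is needed. Follow-up continues, and neither section states a consequence for the analysis.

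Section 7.3.1 records concomitant medications at Day 22 and draws a fluconazole level with no restriction by arm. Exploratory Outcome 9 in Section 3.2.3 uses that level only as "The proportion of subjects with a detectable fluconazole level as assessed by blood test on Days 22 and 43 in fluconazole recipients".

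Section 11.4.4.1 says that sensitivity analyses may be performed. It names drop-out, censoring mechanisms and analysis methods, and does not name prohibited medication.

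**The concern.** The primary objective compares fluconazole with placebo in cases adherent to their assigned product. A placebo case on outside fluconazole is not a clean placebo observation, yet the stated rules treat it as one. Section 11.4.1 itself groups per-protocol subjects by the product actually received after a randomization or dispensing error, so the omission sits badly with the plan's own per-protocol logic.

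The event is foreseeable. Section 2.3.1 warns that subjects who stay unwell may seek further antimicrobial treatment, and serology results are withheld until Day 43. Section 11.2.2 takes dilution of the effect seriously, but only from case misclassification.

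At stake is a diluted effect in the primary test, and in the conditional-power futility looks in Section 11.3.2 that use the same endpoint.

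**Working it through.** **Does pill adherence already filter these subjects?** Two capsules a day for 21 days is 42 capsules. 0.80 × 42 = 33.6, so 34 capsules (17 full days) suffice, and a subject can miss the last 4 days and still pass. One who keeps taking placebo capsules alongside an outside antifungal is fully adherent. One who stops capsules earlier falls below 80% only if expected pills keep accruing after discontinuation, which the text does not define. The filter is partial.

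**Inputs** (Section 11.2.1):
- Response rates: "the clinical response proportion at Day 22 will be 0.20 in the placebo arm, and 0.40 in the fluconazole arm".
- Size: "enrollment will continue until 200 subjects are evaluable for efficacy, 100 in each treatment arm".
- Test and level: "to compare proportion of clinical responses at Day 22 at the two-sided level of 0.05".
- Stated result: "which suffices for 88% power for the Z test with unpooled variance".

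**The plan's own figure.** Power = Φ(d/SE − 1.96), with SE = √[p₁(1−p₁)/n₁ + p₀(1−p₀)/n₀].
- SE = √(0.40×0.60/100 + 0.20×0.80/100) = 0.0632.
- d/SE = 0.20/0.0632 = 3.162.
- Power = Φ(1.202) = 88.5%.

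With the pooled null variance the result is 87.6%, the Table 5 value. The stated power reproduces; it assumes no outside antifungal use on placebo.

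**Model.** Let x be the share of placebo per-protocol cases using an outside antifungal. The documents give no value for x.
- *Kept, full benefit:* users respond at 0.40, so p₀ = 0.20 + 0.20x.
- *Kept, half benefit:* users respond at 0.30 (an assumption for partial exposure), so p₀ = 0.20 + 0.10x.
- *Excluded:* n₀ = 100(1−x), with p₀ assumed to stay at 0.20.
- *Coded as non-responders:* p₀ = 0.20(1−x).

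Worked for x = 10%:
- Kept, full benefit: p₀ = 0.22, d = 0.18, SE = √(0.0024 + 0.001716) = 0.0642, d/SE = 2.806, power = Φ(0.846) = 80.1%.
- Excluded: n₀ = 90, SE = √(0.0024 + 0.16/90) = 0.0646, d/SE = 3.094, power = Φ(1.134) = 87.2%.

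| x | Difference if kept (full benefit) | Power: kept, full benefit | Power: kept, half benefit | Power: excluded | Power: non-responder |
|---|---|---|---|---|---|
| 0 | 0.20 | 88.5% | 88.5% | 88.5% | 88.5% |
| 5% | 0.19 | 84.7% | 86.7% | 87.9% | 91.7% |
| 10% | 0.18 | 80.1% | 84.7% | 87.2% | 94.2% |
| 20% | 0.16 | 69.2% | 80.1% | 85.4% | 97.5% |

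**What non-responder coding does under the null.** The last column exceeds the uncontaminated 88.5%, which is a warning. Suppose true response is 0.20 in both arms and users occur only on placebo. At x = 10% the coded placebo rate is 0.18.
- SE = √(0.20×0.80/100 + 0.18×0.82/100) = 0.0555.
- d/SE = 0.02/0.0555 = 0.361.
- The chance of a significant result favouring fluconazole is Φ(0.361 − 1.96) = 5.5%, against a nominal 2.5%.

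At x = 5% it is 3.7%. Exclusion leaves it at 2.5% if outside use is unrelated to prognosis.

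**The case against.** Several points on the other side have weight.

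- **The current bias is conservative.** Keeping users as observed pulls toward no difference and does not inflate the false-positive rate. This stands, and it is why a reader who infers that users should simply be failures in the primary analysis goes too far: that swaps a conservative bias for one favouring fluconazole.
- **Exposure before Day 22 may be short.** Section 2.2 describes antifungal treatment as usually following failed antibacterials, and someone who stopped capsules around Day 18 would have had only a few days of outside drug. Full benefit is therefore an upper case, and the half-benefit column is shown beside it.
- **There is no observed rate.** Section 2.1 reports that "896 (18%) were known to be tested for coccidioidomycosis, although the proportion tested varied ranged 5% to 39% by facility". A reader might take these figures as a ceiling on contamination. They are testing rates in all pneumonia patients over two months, not treatment rates in serologic cases by Day 22. They show that local testing happens and bound nothing.
- **Some users leave through adherence.** This is true for those who stop capsules early, subject to the undefined expected-pill count.
- **Details are deferred.** Section 11.4.4 leaves efficacy details to a separate SAP, which is not in the text reviewed and could add a rule. Section 11.4.1 is nevertheless the governing population definition, and it is silent.
- **Exclusion is a post-randomization selection.** This also stands. If users are the patients doing badly, removing them could raise the remaining placebo response rate. Hence the two sensitivity analyses.

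**Conclusion.** The gap is real. The documents prohibit outside systemic antifungals and record their use, but no rule links that use to per-protocol membership or response coding. Placebo users can stay in the primary analysis, and if the antifungal works the effect is biased toward the null.

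The size is unknown. Under the plan's own rates with 100 per arm, power falls from 88.5% to 84.7% at 5% use and 80.1% at 10% if users gain full benefit, or to 86.7% and 84.7% if they gain half.

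Three stronger readings are not supported:
- That the stated 88% is wrong. It reproduces.
- That only placebo subjects can be affected. Fluconazole recipients can also take outside antifungals, though this should disturb the contrast less.
- That a single fluconazole dose is allowed on treatment. Section 6.6 ties that exception to the four weeks before enrollment, through Exclusion Criterion 6.

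The change is worth making because it is cheap and concerns the primary analysis, not because a large loss has been shown.

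**What to change.** In Section 11.4.1, and before any unblinding, including the unblinded futility looks:

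1. Exclude from the per-protocol populations, in both arms, any subject whose concomitant-medication record shows a systemic antifungal other than study product between Day 1 and the Day 22 assessment. Do not carry over the pre-enrollment single-dose exception.
2. Report the number excluded by arm.
3. Pre-specify two sensitivity analyses: one keeping these subjects as observed and one coding them as non-responders. Do not make non-responder coding the primary rule.
4. Use a detectable Day 22 fluconazole level in placebo recipients as a supportive check, handled by the SDCC only. It should not define exclusion, because it cannot reveal outside use in the fluconazole arm.
5. Count excluded subjects as not evaluable in the blinded enrollment reassessment of Section 11.3.3.

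The cost is protocol and SAP wording; the medication records and blood samples are already collected. The downside is a slightly smaller per-protocol set (87.2% power at 10% placebo use if enrollment is not topped up) and one more post-randomization exclusion.
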